Discussion: this study will evaluate the diagnostic quality of CIPA vs the GLIM criteria for malnutrition and will establish the prevalence of sarcopenia in inpatients.

Trial registration:

Keywords: nutrition assessment, inpatient, sarcopenia, GLIM, CIPA, screening, body composition, phase angle, hospital stay, mortality.

Background

Malnutrition is a poor prognostic factor for the inpatient. It can contribute to increase the number and severity of the complications of the disease itself, to weaken the response capacity to treatment, increase its morbidity and mortality and the healthcare cost. Numerous research papers corroborate that nutritional intervention can improve the clinical evolution of hospitalized malnourished patients, making early diagnosis of hospital malnutrition (HM) of vital importance [1].

HM is a frequent problem in patients admitted to a hospital. Prevalences ranging between 10% and 50% have been observed, depending on the type of patients analyzed, the category of hospital where they are admitted, and the nutritional assessment markers used for their evaluation. In Spain, the multicenter PREDYCES study conducted in more than 1700 patients, found that 23.7% of hospitalized patients are malnourished or at nutritional risk [2], while the recent seDREno study used to the nutritional evaluation of the GLIM malnutrition criteria, and observed that 29.7% of hospitalized patients are malnourished [3].

There are many nutritional screening methods validated in the hospitalized population, but none meet all the suitability criteria, so there is no gold-standard that favors their widespread implementation in the different hospital centers. At Hospital Universitario Nuestra Señora de la Candelaria (HUNSC) in Tenerife, a nutritional screening method called CIPA (Control of Intakes, Proteins and Anthropometry) was designed, which has covered several phases in its development and validation. In this, different items are evaluated: a) decrease in

intake <50% in 72h; b) plasma albumin <3 g/dl; and c) BMI < 18.5 kg/m², mid-upper arm circumference (MUAC) ≤22,5 cm (if the BMI cannot be determined). Positivity of at least one of these items would result in a positive CIPA nutritional screening and would identify the patient with malnutrition or at risk of suffering from it. Since 2015 it has been implemented in the HUNSC, carrying out different validation, optimization and cost effectiveness studies [4–11].

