The GLIM criteria (Global Leadership Initiative on Malnutrition) aim to provide a consensus at a global level that allows for common criteria for the diagnosis of malnutrition and, in this way, the results obtained through their application can be compared. It is a two-step strategy: first, a validated screening test would be applied to identify malnourished patients or patients at risk of malnutrition and, later, the second step would be carried out, which consists of the diagnostic evaluation of malnutrition and graduation of malnutrition. To evaluate the diagnosis and degree of malnutrition, phenotypic criteria (unintentional weight loss, BMI and reduction in muscle mass) and etiological criteria (decrease in intake and presence of inflammation) are used. A patient would be identified as malnourished when he presents at least 1 phenotypic criterion and 1 etiological criterion. The severity of malnutrition would be assessed using phenotypic criteria [12].

As a result of the publication of these criteria, different studies have been developed that evaluate the sensitivity and specificity of different nutritional screening tools and/or nutritional evolution with respect to GLIM [13]. However, most are not comparable because they are heterogeneous samples and in different areas of medical care.

Another aspect of great interest at the present time is the evaluation of cellular and muscular functionality and its prognostic implications. For the evaluation of cell function, the phase angle has been developed in recent years. It is obtained through the realization of bioimpedance, being the result of the ratio between reactance and resistance. It has been postulated as an indicator of cell integrity and an early marker of malnutrition [14]. On the other hand, muscle functionality can be assessed using dynamometry. It is a simple and accessible technique that

quickly assesses muscle function. In addition, the determination of these parameters (including muscle mass, also given by bioimpedanciometry), would allow us to know the prevalence of sarcopenia that is associated with the appearance of adverse events such as falls, fractures, physical disability and mortality [15].

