This study will provide us with information about the diagnostic quality of the nutritional screening carried out in our environment compared with the GLIM criteria for malnutrition. In addition, by comparing the prevalence of sarcopenia and the phase angle in patients with positive or negative screening, we will be able to estimate the risk of muscle and cellular dysfunction in patients with the worst clinical prognosis.

Methods

Trial design:

Cross-sectional single-center study comparing the diagnostic quality of the CIPA instrument in the diagnosis of malnutrition or risk of presenting it in hospitalized patients vs GLIM and subsequent prospective follow-up of patients for up to six months.

The aims:

Primary endpoint:

- Determine the diagnostic quality of the CIPA tool, in inpatients with stays longer than three days, in the observation of risk of malnutrition compared to the gold standard GLIM as a diagnosis of malnutrition.

Secondary endpoints:

- Determine the positive and negative predictive values in comparison to the selected gold standard.
- Determine the degree of reliability, likelihood ratio and diagnostic odds ratio of the tool compared to the gold standard.

- Determine the point of greatest balance between sensitivity and specificity for each of the three variables that make up the diagnostic instrument for malnutrition.
- Determine the degree of Kappa concordance between both diagnostic criteria (CIPA vs. GLIM).
- Establish the cut-off point for the phase angle of the population studied by bioimpedanciometry for men and women, and determine prognostic values according to the optimal cut-off point.
- Evaluate prognostic variables (mortality, average stay, readmission rate) according to the two tools under study (CIPA vs. GLIM) at discharge, together with early readmissions, and mortality at six months of prospective follow-up.
- Evaluate whether CIPA positive subjects obtain worse muscle functionality results according to dynamometry than CIPA negative subjects.
- Determine if there is a relationship between positive CIPA and sarcopenia according to established EWGSOP2 diagnostic criteria.
- Determine if there is a relationship between positive subjects with sarcopenia vs negatives in relation to the six-month prognosis.

Inclusion criteria:

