For the cross-sectional study of the quality of diagnostic criteria between the CIPA instrument and the current gold standard GLIM, a study of sensitivity, specificity, positive and negative predictive values, as well as the likelihood and an estimator of a single value such as the diagnostic odds ratio. In addition, they will determine the best equilibrium points for the three items of the CIPA instrument according to the Youden model, determining in each case the area under the curve (AUC). Likewise, the concordance between both CIPA tests and the GLIM gold standard will be determined by the Kappa coefficient according to Cohen's model. All point estimates will be accompanied by 95% confidence intervals.

For the follow-up study with CIPA positive patients, an initial univariate study of the factors that could determine prognostic levels in the patients will be carried out. These analyzes will be parametric/non-parametric according to the homoscedasticity and normality of the data in each distribution, analyzed by the Kolmogorov-Smirnov test. Subsequently, for the variables with statistical significance or clinical relevance found in the univariate analysis, multivariate models will be carried out with the aim of knowing the one that best fits the data and determining the prognostic factors in the patients studied. The selection of the final model will be guided by the principle of parsimony. Collinearity will be evaluated by the main regression component of the explanatory variables. While

the different models will be compared by the likelihood ratio and the Wald test. The existence of confusion will be evaluated by clinical criteria with a significant change of 10% over the coefficient obtained according to the variables included in the model. The model will be validated by the Hosmer-Lemeshow calibration test and by the area under the curve (AUC) as a measure of discrimination.

Workplan:

This study will select patients with an expected hospital stay of more than three days, through probabilistic sampling to control possible biases in the selection of subjects. The selection will be made in the departments specified by physicians or personnel trained for this purpose, establishing whether they meet all the established inclusion criteria and none of the exclusion criteria, according to the study protocol. Each patient will receive a full explanation of the study objectives and an informed consent form will be signed.

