Once the patient is selected and coded to ensure data protection, after three days of stay, according to the usual protocol, the risk of malnutrition will be studied with CIPA and, later, GLIM will be performed on these patients.

For the evaluation of cell function, the phase angle obtained by bioimpedanciometry (Aker BIA 101 Anniversary) will be used and observing the ratio between reactance/resistance between body cell mass and fat-free mass. Likewise, muscular functionality will be evaluated by dynamometry (using a Jamar dynamometer), taking the maximum value of between two measurements in the dominant arm with an interval of at least one minute between one and the other. In turn, the values under study will be collected and the the data collection notebook according to coding. The risk of sarcopenia will be determined according to values observed in dynamometry and bioimpedance measurement established in the 2019 European consensus on Sarcopenia according to the EWGSOP2 criteria: grip strength determined by dynamometry, positive in males if < 27 kg and in women if < 16 kg, muscle volume, determined by bioimpedance analysis, positive if appendicular skeletal muscle mass < 20 kg in men and < 15 kg in women.

All subjects with a positive test according to the CIPA instrument will be treated according to the usual protocol to correct possible malnutrition or risk thereof,

while subjects with a negative CIPA test but a positive GLIM will be studied and constantly monitored, taking the appropriate measures according to criteria. optional. Patients will be followed up during their hospital stay and 6 months after discharge, prospectively collecting variables for the study of prognostic factors (hospital stay, early readmission rate, mortality).

The study consists of a first cross-sectional part that will be completed once the data of the 490 subjects selected through probabilistic sampling has been collected. The second part of the study will consist of the prospective follow-up of the patients and the variables will be analyzed with prognostic criteria. In these cases, follow-up will end 6 months after discharge. Thus, the total estimated months to complete the study is estimated at 15 months. The study will be conducted entirely at HUNSC.

Difficulties and limitations of the study:

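### Item-wise Youden cut-offs are chosen in the same 490 patients with no internal validation, so any sensitivity, specificity or J reported at those points would on average be too favourable (minor, secondary objective)

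*Combined protocol and SAP*

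**What the plan says.** One secondary endpoint under The aims is to "Determine the point of greatest balance between sensitivity and specificity for each of the three variables that make up the diagnostic instrument for malnutrition". The section Statistical analysis of the data carries this out: "they will determine the best equilibrium points for the three items of the CIPA instrument according to the Youden model". For each item it also plans an area under the curve. It adds: "All point estimates will be accompanied by 95% confidence intervals".

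The Workplan describes one sample at one hospital, "a first cross-sectional part that will be completed once the data of the 490 subjects" have been collected. The cut-offs are therefore chosen, and anything reported at them is evaluated, in the same patients.

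The analysis section mentions validation once: "The model will be validated by the Hosmer-Lemeshow calibration test and by the area under the curve (AUC) as a measure of discrimination". That sentence closes the paragraph on the multivariate prognostic models of the follow-up part and does not reach the item cut-offs.

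**The concern.** A Youden cut-off is the value at which the observed sum of sensitivity and specificity is largest. It follows chance features of the sample as well as the true separation between GLIM-positive and GLIM-negative patients. When accuracy at that value is read back from the same sample, the chance part is counted as performance. An interval that treats the cut-off as fixed ignores the selection and tends to cover less than its nominal 95%.

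At stake is how a reader judges the item-level results. Each item could look somewhat more accurate at its new point than it is, with an interval that is too optimistic, and the point could look more settled than it is.

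**Working it through.** **Inputs.** N = 490 (Workplan). The plan gives no formula or inputs for this number, so it is taken as given. GLIM prevalence is an assumption: a Spanish inpatient survey cited in the Background "observed that 29.7% of hospitalized patients are malnourished", and 0.297 × 490 ≈ 146 positive, leaving 344 negative. The documents give no item AUC. The Discussion reports 0.63 to 0.80 for whole tools against GLIM in other populations, so 0.60 to 0.80 is assumed.

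**Direction.** At any fixed cut-off c, the observed J(c) is unbiased. The observed maximum is at least the observed J at the truly best cut-off, so its expectation is at least the true maximum. The true maximum is in turn at least the true J at the cut-off actually chosen. Hence the reported J is too high on average. The AUC uses all thresholds and selects none, so this step does not bias it, provided the direction of each item is fixed in advance, as it is in CIPA.

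**Size, continuous item.** The model is equal-variance binormal with d = √2·z(AUC). The cut-off c is the empirical Youden point, and the true value is J = Φ(c) − Φ(c − d). There were 3000 simulated data sets per AUC. The ordinary interval for J is the Wald interval, with half-width 1.96·√[Se(1−Se)/146 + Sp(1−Sp)/344].

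| AUC | Reported J | True J | Overstatement | Coverage of ordinary 95% interval |
|---|---|---|---|---|
| 0.60 | 0.181 | 0.132 | 0.049 | 84.1% |
| 0.65 | 0.250 | 0.205 | 0.045 | 86.0% |
| 0.70 | 0.320 | 0.280 | 0.040 | 86.7% |
| 0.75 | 0.395 | 0.358 | 0.037 | 86.2% |
| 0.80 | 0.474 | 0.440 | 0.035 (before rounding) | 87.5% |

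The mean half-width runs from 0.091 to 0.084 over this range, so the overstatement is 0.049/0.091 ≈ 0.54 to 0.035/0.084 ≈ 0.42 of it. Sensitivity is overstated by 0.025 to 0.034 and specificity by 0.010 to 0.015. Their ordinary intervals cover 89 to 92% and 92 to 94%. The AUC bias is at most 0.0005. A separate simulation gave an overstatement of J of 0.047, 0.039 and 0.034 at AUC 0.63, 0.731 and 0.80, with J too high in 81 to 87% of samples.

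**Sensitivity to the assumptions** (overstatement of J; coverage of the ordinary interval):
- Prevalence 10%, 23.7% or 50% (Background figures): 0.032 to 0.082; 80 to 88%.
- Standard deviation ratio 0.67 or 1.5: 0.031 to 0.039; 85 to 89%.
- Ten possible thresholds: 0.020 to 0.033; 92 to 94%.
- Three or four thresholds: 0.006 to 0.026; 94 to 95%.
- Item recorded yes/no: no bias.
- Item that is itself a GLIM criterion, modelled as a step at the GLIM threshold: 0.007 to 0.038; 87 to 94%. This matters for BMI and intake, because the Background says of GLIM: "phenotypic criteria (unintentional weight loss, BMI and reduction in muscle mass) and etiological criteria (decrease in intake and presence of inflammation) are used".

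MUAC used in place of BMI was not modelled.

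**Does the remedy work?** The bootstrap optimism correction repeats the cut-off search in every resample (600 data sets × 200 resamples per AUC). It moves mean J from 0.182 to 0.147 against a true 0.133 at AUC 0.60, and from 0.473 to 0.448 against 0.439 at AUC 0.80. The remaining bias is 0.014 and 0.009. An interval of ordinary Wald width centred on the corrected J covers 92 to 96%, against 89 to 92% for one built from bootstrap optimism quantiles. Recentred intervals for sensitivity and specificity cover 93 to 95% and about 94%.

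A percentile interval for the cut-off itself covers 96 to 98% in the continuous model. In the step model it covers only about 67 to 73% when 10% of patients lie beyond the GLIM threshold, 87 to 88% at 20%, and 90 to 93% at 30%.

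**The case against.** The strongest objection is that the harm depends on an output the plan does not list. Sensitivity, specificity and predictive values are planned for CIPA as a whole; for the items only the cut-off and the AUC are named. This stands. That item-level accuracy will be reported is an inference from the objective, which defines each point by the balance of the two measures.

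A second objection is that the size rests on facts the documents leave open. This also stands. The Background states intake as a criterion that is met or not, while Data Collect speaks of a percentage; if intake is recorded yes/no, nothing is left of the concern for that item. The direction of the bias for any item with several thresholds does not depend on those facts.

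A third is that the analysis section names no interval method for any estimate, so its silence on an interval for the cut-off is not peculiar to this step. That is right, and the silence is not counted as a separate fault here.

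A reader might also take the instability of the cut-off as further proof of optimism. At AUC 0.70 the true sensitivity at the chosen point ranges from 0.44 to 0.81. But this is movement along a flat maximum, traded against specificity: true J ranges only from 0.243 to 0.289, where 0.289 is the best attainable. It shows that the cut-off is poorly determined, not that accuracy is overstated by that much.

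**Conclusion.** The concern holds as a minor point on a secondary objective. If sensitivity, specificity or J is given at an item's Youden point, it will on average be too favourable. For J this is about 0.035 to 0.05, with ordinary intervals covering about 84 to 88%, assuming 29.7% prevalence, a continuous item and an AUC of 0.60 to 0.80. The effect shrinks with few categories and vanishes for a yes/no item.

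Three stronger readings are not supported. The bias does not favour the item in every sample: J was too high in roughly 80 to 90% of simulated samples. It does not extend to the item AUCs; overlap of BMI and intake with GLIM may raise those, but that is a different question. And it does not touch the primary comparison, which uses CIPA cut-offs fixed before the study.

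**What to change.** In Statistical analysis of the data, after the Youden sentence, add:

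1. The item cut-offs are exploratory.
2. Wherever sensitivity, specificity or J is given at an item's Youden point, the bootstrap optimism-corrected value is reported, with the cut-off search repeated in every resample. Its 95% interval has the ordinary width (Wald for J) and is centred on the corrected value.
3. The spread of the selected cut-off over the same resamples is shown as a description of its instability, not as a guaranteed 95% interval, because for items that are themselves GLIM criteria the percentile interval can cover well below 95%.

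Leave the AUC analysis as planned. No clinical cut-off is proposed here.

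The cost is two or three sentences and a short bootstrap, with no new data. The reported figures will be slightly less favourable, and the correction is incomplete: a bias in J of about 0.01 to 0.02 should be expected to remain.

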The participation of the patients in the study will consist of performing the screening for malnutrition that is usually used in the hospital (CIPA) to which the GLIM test will be added, considered as the gold standard for this work. The scores of both tests will be recorded together with the data collection through the clinical history or with direct questions to the patient.

For the CIPA test, the BMI, albumin levels and percentage of decreased intake will be taken. For the GLIM test, phenotypic criteria such as non-voluntary weight loss and reduction in muscle mass will also be studied together with etiological criteria to which, in addition to those mentioned for the CIPA test, the presence of inflammation will be added.

Together with the usual work protocols and data depending on the pathology under treatment, the variables collected will be: age, sex, cause of admission, comorbidity, functionality, interventions or treatments per admission, bioimpedance testing, dynamometry, presence of sarcopenia.

Subsequently, the sample of patients with a positive CIPA (as it is currently considered the screening test used in the hospital) will be implemented the therapeutic measures according to the usual protocol, while the subjects with a negative CIPA test but a positive GLIM will be studied. and constant monitoring taking the appropriate measures according to optional criteria. The patients will be followed up for the study of prognostic factors based on the variables obtained.

Statistical analysis of the data:

The data will be recorded in the data recording notebook and imported once the study is closed to specific software for statistical treatment (STATA SE 14; SPSS, V21). The descriptive analysis of the data will divide the variables into qualitative and quantitative. Obtaining means and standard deviations for the quantitative variables and frequencies and proportions for the qualitative data. Graphs will be obtained for a better understanding of the results.

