The possible difficulties of the study will focus on the time of inclusion of subjects due to the large number of sample used. Likewise, special attention will be paid to the follow-up of subjects during their hospital stay, not assuming a number of patients with simultaneous stays greater than what the components of the research project can manage.

Ethical aspects and confidentiality:

The study will be carried out in accordance with the requirements expressed in the Declaration of Helsinki [revision of Fortaleza (Brazil), October 2013] and the Laws and Regulations in force in Europe and Spain.

The information sheet will be delivered to the participating subjects. The investigator will explain to the patient the objectives and procedures of the study, and will request the signing of the informed consent form. Once the consent is signed, the researcher will begin the explorations and data collection necessary for the study. The investigator will not initiate any investigation corresponding to the study until the consent of the patient has been obtained.

The treatment, communication and transfer of personal data of all participating subjects will comply with the provisions of Organic Law 3/2018, of December 5, Protection of Personal Data and guarantee of digital rights, and the application of Regulation (EU) 2016/679 of the European Parliament and of the Council of April 27, 2016 on Data Protection (RGPD).

To maintain patient confidentiality, no demographic data that could identify the subject will be collected (e.g. initials, date of birth). To protect the identity of the patient, a unique number will be assigned to each subject and their related records.

In order to guarantee the confidentiality of the data of the patients participating in the study, only the researcher and his team of collaborators, the representative of the promoter who will carry out the monitoring tasks, the auditor in the event that the study was submitted to an audit, the CEIm and the Health Authorities.

Discussion:

This study evaluates the diagnostic quality of the CIPA nutritional screening with respect to the GLIM criteria for malnutrition and its prognostic implications, as well as the functionality and cellular vitality by bioimpedance analysis and the presence of sarcopenia. For this, the CIPA nutritional screening will be carried out and the phenotypic and etiological variables will be evaluated to apply the GLIM criteria.

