In previous studies, a slight-moderate correlation has been observed between nutritional screening methods and the GLIM criteria. Boulhosa et al studied patients with advanced chronic liver disease comparing NRS-2002 with GLIM. They obtained a Kappa index of 0.43 and an AUC of 0.731 [16]. Clark et al compared MST vs. GLIM, sensitivity was 56.7%, specificity 69.0%, AUC 0.63, and kappa index 0.26 [17]. For their part, Bellanti et al. compared GLIM with MUST, VGS and NRS-2002 in a sample of 152 hospitalized geriatric patients, obtaining a sensitivity of 64%, 96% and 47%, and a specificity of 82%, 15% and 76%, AUC of 0.80, 0.77 and 0.69, respectively. In turn, the agreement with GLIM was 89%, 53% and 62% for the MUST, VGS and NRS-2002 [18]. The good correlation of MUST with GLIM can be explained by the degree of similarity between the two tests, since the MUST determines the BMI, percentage of weight loss, presence or absence of inflammation or acute diseases, and these parameters are included. inside the lim. Likewise, the high sensitivity of the VGS is due to the fact that it is not a screening method, but a more specific nutritional assessment, such as the GLIM, and where criteria are similar to the phenotypic and etiological ones. In any case, as can be seen, they are different populations in which it is not convenient to compare or combine the findings.

As for sarcopenia, it is also a pathology with a high prevalence. Ballesteros et al. [19] studied hospitalized patients from the Spanish population, determining a

probable prevalence of sarcopenia of 33%, confirmed by determining muscle mass in 22.5%. Lengelé et al [20] observed a higher risk of sarcopenia in patients diagnosed with malnutrition using the GLIM criteria (HR 3.19 (95% CI 1.56 – 6.5) [20] and Bellanti et al [18] observed that patients with a high risk of malnutrition determined by MUST are also more likely to present sarcopenia (OR 2.5, CI 1.3-3.6).

As for the limitations, we find ourselves with an ambitious study in which a large sample is to be recruited, and it may be assumed that the time necessary for the inclusion of the subjects in the study and data collection is delayed. On the other hand, perhaps the representation of patients admitted to surgical areas may be limited since the need for artificial nutrition prior to performing nutritional screening has been included as an exclusion criterion, the need for this being greater in complex surgical patients.

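### The planned BMI and intake cut-offs and AUCs are scored against a GLIM reference that itself contains BMI and intake, so these two results are partly circular, and the plan does not state this as a limitation for CIPA

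*Combined protocol and SAP*

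**What the plan says.** The Background defines CIPA by three items: intake, albumin and BMI (arm circumference if BMI cannot be obtained). "Positivity of at least one of these items would result in a positive CIPA nutritional screening". For GLIM, it says that "phenotypic criteria (unintentional weight loss, BMI and reduction in muscle mass) and etiological criteria (decrease in intake and presence of inflammation) are used", and a diagnosis needs at least one criterion of each kind.

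A secondary endpoint is to "Determine the point of greatest balance between sensitivity and specificity for each of the three variables that make up the diagnostic instrument for malnutrition". The statistical analysis section repeats this: "they will determine the best equilibrium points for the three items of the CIPA instrument according to the Youden model", with an AUC each time. GLIM is the declared gold standard and the only reference named.

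Data Collect describes the GLIM data as an addition to the CIPA data, with "etiological criteria to which, in addition to those mentioned for the CIPA test, the presence of inflammation will be added". The Workplan says that "the risk of malnutrition will be studied with CIPA and, later, GLIM will be performed on these patients".

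The Discussion is aware of the mechanism for another tool: "The good correlation of MUST with GLIM can be explained by the degree of similarity between the two tests". It makes a similar remark about the subjective global assessment. Neither remark is applied to CIPA. The limitations section opens with "The possible difficulties of the study will focus on the time of inclusion of subjects due to the large number of sample used" and goes on to follow-up workload. The Discussion adds possible delay and limited representation of surgical patients.

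**The concern.** When a variable is part of the reference standard, its ROC curve against that standard partly measures the variable against itself. This applies to BMI and, by inference, to intake. Albumin has no such built-in advantage.

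Two readings of the results are at stake. A good BMI or intake AUC could be taken as independent support for that item. The three AUCs could also be ranked as if they had been earned on the same terms. In addition, the Discussion hopes to learn when the fuller GLIM assessment is needed. A single sensitivity or kappa does not show which GLIM components CIPA misses.

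**Working it through.** **No plan figure to reproduce.** The documents give no expected AUC, component prevalence, correlation or operational GLIM threshold. The sample size of 490 comes without inputs, and this point does not depend on it.

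**Step 1: components side by side.**

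| Item | In CIPA | In GLIM (Background list) |
|---|---|---|
| BMI | yes, below 18.5 kg/m² | yes, phenotypic; cut-off not given |
| Intake | yes, below 50% in 72 h | yes, etiological; window and cut-off not given |
| Albumin | yes, below 3 g/dl | not listed |
| Weight loss, muscle mass, inflammation | no | yes |

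Two of CIPA's three items are named GLIM criteria.

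**Step 2: the mechanism by hand.** Assume independent components with these prevalences: low BMI 0.10, weight loss 0.25, low muscle mass 0.25, low intake 0.30, inflammation 0.40. BMI and intake then carry no information about the other criteria, so their AUC against GLIM with the item removed is 0.50.

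- P(any etiological) = 1 − 0.70 × 0.60 = 0.58.
- P(any phenotypic, BMI not low) = 1 − 0.75 × 0.75 = 0.4375.
- P(GLIM+) = 0.10 × 0.58 + 0.90 × 0.4375 × 0.58 = 0.0580 + 0.2284 = 0.2864.
- BMI at GLIM's own threshold: sensitivity 0.0580 / 0.2864 = 0.2025; false-positive rate 0.10 × 0.42 / 0.7136 = 0.0589.
- The ROC curve is two straight segments meeting at that point, so AUC = ½ (1 + 0.2025 − 0.0589) = 0.572. The Youden optimum is GLIM's threshold itself.
- Intake: P(any phenotypic) = 1 − 0.90 × 0.75 × 0.75 = 0.4938; sensitivity 0.30 × 0.4938 / 0.2864 = 0.517; false-positive rate 0.30 × 0.5062 / 0.7136 = 0.213; AUC = ½ (1 + 0.517 − 0.213) = 0.652.

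A simulation of 400,000 patients gave 0.572 and 0.651, against 0.500 and 0.499 with the item removed. Uninformative items therefore score above 0.50 purely through the overlap.

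**Step 3: correlated components.** All inputs here are assumptions: weight loss 25%, low muscle mass 15%, BMI mean 26.5 and SD 5.5, and a common latent correlation of 0.2 or 0.4. The 27 settings cross GLIM BMI cut-offs of 18.5, 20 and 22, inflammation of 30, 50 and 70%, and GLIM low intake of 15, 25 and 40%.

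| Correlation | BMI AUC, full GLIM | BMI AUC, GLIM without BMI | Intake AUC, full GLIM | Intake AUC, GLIM without intake |
|---|---|---|---|---|
| 0.2 | 0.68–0.76 | 0.62–0.64 | 0.64–0.77 | 0.62–0.63 |
| 0.4 | 0.76–0.83 | 0.72–0.75 | 0.74–0.83 | 0.73–0.74 |

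Within settings, the BMI excess was 0.042–0.139 at correlation 0.2 and 0.026–0.107 at 0.4. The intake excess was about 0.01–0.14 over both. Every difference was positive.

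**Step 4: sensitivity to the equal-correlation assumption.** BMI and muscle mass are both body-size measures. Raising only their correlation to 0.7 cuts the BMI excess to about 0.01–0.09 and leaves the intake excess almost unchanged.

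**Step 5: the BMI cut-off.** With equal correlations, the Youden cut was 22.0–24.3 (correlation 0.2) and 23.3–25.1 (0.4) against full GLIM, compared with 25.8–26.2 and 25.3–25.9 against GLIM without BMI. With the BMI–muscle correlation at 0.7, the shift was 0–2.0 and 0–1.4 kg/m², and zero in some settings. With 490 patients, the simulated SD of the cut was about 1–2 kg/m². The AUC difference is better estimated (SD 0.010–0.019 for BMI, 0.006–0.021 for intake).

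**Step 6: albumin.** Against full GLIM, its AUC was 0.62–0.64 (correlation 0.2) and 0.73–0.75 (0.4) under equal correlations. With an assumed albumin–inflammation correlation of 0.6, it was 0.655–0.727 and 0.738–0.789. Its level depends on an input that the documents do not give.

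**The case against.** The strongest reply is that a cut-off for a tool meant to detect GLIM malnutrition should be tuned to GLIM as it stands. Removing a criterion changes the question, and no section claims that the item AUCs validate BMI or intake independently. The components of both rules are openly listed, and the component data are being collected anyway.

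Much of this stands. Full GLIM is the right primary reference, and the item-removed analyses can only be secondary. The reply does not make the three AUCs comparable, and it does not explain why shared content is used to interpret another tool's agreement but is not mentioned for CIPA.

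A reader might infer four stronger things that the documents do not support:

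- **That the overlap undermines the primary comparison.** It does not; agreement with full GLIM is what that aim asks for.
- **That the BMI cut-off will simply return GLIM's threshold.** This follows only when the items are uncorrelated. Otherwise the shift can be zero.
- **That albumin's AUC shows what the other items would score without overlap.** That result comes from assuming equal correlations. The wording in Data Collect is also loose enough to leave albumin's role in GLIM unclear, and should be reconciled with the Background list.
- **That intake is certainly the same measurement in both tools.** GLIM is done after CIPA, and its intake definition is not stated.

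**Conclusion.** The point holds as a matter of interpretation and reporting. The BMI overlap is plain from the documents; the intake overlap is a reasonable inference. The direction is an upward shift in both AUCs. The size is unknown: the illustrations give about 0.01–0.14 for each item at latent correlations of 0.2–0.4, and 0.01–0.09 for BMI if it correlates at 0.7 with muscle mass. These figures rest wholly on assumed prevalences, correlations and GLIM cut-offs, and they are not bounds. Movement of the BMI cut-off toward GLIM's threshold is possible but cannot be predicted with confidence. This is an inexpensive improvement to consider, not a flaw in the primary analysis.

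**What to change.** - Keep full GLIM as the primary reference.
- State the shared BMI and intake criteria as a limitation for CIPA, and do not present the full-GLIM AUCs of these items as independent support for them.
- Cross-tabulate which components made CIPA positive and which made GLIM positive, including GLIM-positive patients whom CIPA misses.
- As secondary sensitivity analyses, report the BMI ROC and Youden result also against GLIM without BMI, and the intake result also against GLIM without intake.

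The cost is a little more analysis of data already collected. The drawback is that an item-removed reference is not GLIM as published and reclassifies some GLIM-positive patients. Under the equal-correlation inputs above, this was about 7–24% without BMI and 2–42% without intake. Some correct detections by the item then count as false positives, which is why these results must stay secondary. A difference between two BMI cut-offs will also be imprecise with 490 patients.
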